**Figure 3: Required DSMB interventions for possible cardiac events.**

Data Category	Variable	DSMB Intervention Level
ECG	1 degree AV block	1
ECG	2 nd Type 1	2
ECG	2 nd type 2	3
ECG	3 rd degree AV block	3
ECG	Sinus tachycardia	1
ECG	Sinus bradycardia	2
ECG	New Bundle branch block	2
ECG	QRS widening>50%	3
ECG	QTc>500msec	3
Holter Monitoring	PVC frequency Increase	2
Holter Monitoring	Nonsustained VT Increase	2
Holter Monitoring	Sustained VT	3
Clinical Symptom	Syncope/unresponsiveness	3

### **Functional Testing:**

In addition to the six minute walk, three timed functional tests have been selected for serial testing. The tests include: placement of pegs in a Purdue peg board for 30 seconds with dominant hand (number placed), the time to walk 30 feet, and time required to "rise up from a chair." These tests reflect specific functional impairments that occur in patients with DM1, specifically: hand weakness (especially finger flexors) and gait impairment due to quadriceps stiffness and weakness and cardiorespiratory functional limitations due to myotonic stiffness and weakness. In addition to these tests, forced vital capacity and serial SF-36 evaluations will be performed at all inpatient visits. Forced vital capacity directly reflects respiratory function while the SF-36 is a widely studied, 36 question, generic health survey index designed to measure functional health and well-being.

### **DM1-Specific Patient Reported Health-Related Quality-of-Life:**

There is an increasing need to demonstrate that potential new treatments being evaluated in therapeutic trials have relevance to patients. To meet this need, over the last two years we have been developing a disease-specific patient reported outcome instrument to measure health related quality-of-life of DM1 patients for use during therapeutic trials. To date, this research has led to the identification, transcription, and coding of over 1100 DM1 patient quotes regarding the highest-impact, most relevant

issues and symptoms for DM1 patients. Under the guidance of the NIH funded PROMIS (Patient-Reported Outcomes Measurement Information System) and Neuro-QoL networks we will soon have a DM1-specific patient reported instrument capable of measuring health-related quality-of-life for this population. This instrument/questionnaire will directly represent the issues of highest importance to patients with DM1; as identified and validated by several hundred DM1 patients. The completion and development of this instrument was carefully planned to abide by the FDA's recommendations for PRO instrument use during clinical trials.[Patrick et al, 2007] Using a patient validated question set this instrument has the capability to measure patient-relevant DM1-specific quality-of-life. In addition, this instrument will be able to measure and tract subdomains of DM1-specific quality-of-life. These subdomains include 1) ambulation; 2) problems with hands or arms; 3) inability to do activities; 4) fatigue; 5) pain, 6) gastrointestinal issues; 7) impaired sleep; 8) emotional issues; 9) cognitive issues; 10) decreased satisfaction in social situations; 11) decreased performance in social situation; 12) myotonia; 13) breathing difficulties; 14) choking issues; and 15) issues related to medicine side effects. A draft version of this instrument is included in the application.

#### **Independent Medical Monitor:**

Dr. [REDACTED], Professor of Neurology at the University of Rochester Medical Center and an international authority on therapeutic trials in neuromuscular disorders, will serve as the independent medical monitor for this study. Dr. [REDACTED] will coordinate his assessments of the laboratory data with the Data Safety Monitoring Board (Dr. [REDACTED] will not serve as a board member of the Data Safety Monitoring Board) overseeing this study and will serve as resource member to that group. The independent medical monitor and the statistical programmer will be unblinded and will review laboratory data and side effects. The independent medical monitor will work closely with the statistical programmer to identify any potential deleterious effects of mexiletine in our patients. Concerns will be discussed as appropriate with the principal investigator. When necessary the blind will be broken and appropriate medical treatment carried out. Because of previous experience in the use of mexiletine, we do not anticipate any major adverse events that will require discontinuation of the study. Additional information regarding the safety monitoring of this study is provided in the Human Subjects Protection portion of this application.

#### **Data Management:**

Study forms, logs, databases, data entry screens, data audit trails, and secure daily computer backups have been developed. The study coordinator will send all forms on a weekly basis to the data manager, who will supervise data entry and verification. Forms relating to adverse events, dosage changes, randomization, terminations, will be faxed to the data manager. Data from DEXA and MViCT measurements will be sent electronically. The manager will track receipt of data and identify missing data. Immediately thereafter this data will be electronically transferred to the statistical programmer. The study coordinator will notify the principal investigator and IRB and follow FDA stipulated guidelines to report any serious adverse events within 24 hours.

All paper copies will be kept in locked cabinets. Additional information regarding the data monitoring of this study is provided in the Human Subjects Protection portion of this application. Some patients may simultaneously participate in the University of Rochester Pathogenesis and Progression in Myotonic Dystrophy Study (RSRB 24971, CRC 1259). In such cases data sharing may take place to minimize redundancy in functional or laboratory testing.

### **Statistical Analyses:**

The primary outcome variable in this clinical trial will be the change from baseline to Month 6 in the mean distance walked during the six minute walk test. Using historical six minute walk test data in the DM1 population, we will have 80% power to detect a group mean change of 183 feet in distance walked over six minutes. The primary statistical analysis will involve fitting a repeated measures analysis of covariance model with treatment group as the factor of interest and the baseline value of the outcome variable as a covariate. The model will also include terms for month (categorical) and the interaction between treatment group and month. An unstructured covariance pattern will be used for model fitting. This model will be used to determine a 95% confidence interval for the adjusted mexiletine – placebo difference in mean response (treatment effect) at Month 6. Confidence intervals for treatment effects at Month 3, as well as averaged over Months 3 and 6, can also be obtained using this model; these will be considered to be secondary analyses.

If clinically important differences are found between the groups at baseline, particularly with regard to important variables such as age, gender, and years since symptom onset, the primary analyses will be repeated after statistically adjusting for these differences. These sensitivity analyses will be considered to be secondary, however.

The underlying assumptions of the analysis of covariance model will be thoroughly checked (e.g., normality, linearity), including analyses of residuals. Remedial measures (e.g., transformations, use of nonparametric methods) will be taken if serious violations of these assumptions are detected.

The primary analyses will be performed according to the intention-to-treat principle and will include all randomized subjects. Every effort will be made to retain subjects in this study and to collect all data at every visit. If a subject cannot tolerate or refuses to continue taking study medication, we will continue to follow and evaluate that subject if he/she is willing. If a subject drops out, attempts will be made to bring the subject in for a final evaluation. Compliance with trial procedures, dropouts/dropins, and reasons for subject withdrawal will be carefully tracked throughout the study. The repeated measures analysis of covariance model above uses maximum likelihood to estimate the parameters of interest (treatment effects) using available data from all subjects. A key assumption underlying this analysis is that the missing data are “missing at random” (MAR), i.e., the probability that responses are missing for a subject depends only on the set of observed data for that subject and not on the specific missing values that were not obtained.

An alternative approach that will be used to deal with missing data in this setting, as a secondary (confirmatory) analysis, is multiple imputation. This will be applied using a regression-based imputation model. For subjects with complete data up to a particular visit, a multiple regression model will be fit that includes the outcome at that visit as the dependent variable and outcomes at previous visits and treatment group as independent variables. Separate models will be similarly constructed for each visit. Using these regression models, a missing value for a subject at a particular visit will be imputed as a draw from the predictive distribution given the outcomes at previous visits (some possibly imputed) and treatment group of the subject. This will be done sequentially starting with the Month 3 visit. This process will be repeated 100 times, resulting in 100 complete analysis data sets. The analyses will be performed separately for each of the 100 complete analysis data sets, and the results will be combined into one multiple imputation inference (estimated treatment effect and associated confidence interval and p-value). This strategy is appropriate for data sets that have a monotone missing pattern. If the data set does not precisely have this pattern, the monotone data augmentation method using Markov-Chain Monte-Carlo will be used to impute the small amount of missing data that is required to make the missing data pattern monotone before applying the multiple imputation algorithm described above. This approach to imputation should be superior to other strategies such as carrying forward the last available observation, which often yields unrealistic imputed values. Also, the use of multiple imputation avoids the problem of artificially increasing power through data imputation associated with single-imputation methods because it accounts for the uncertainty associated with the imputation.

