#### Analysis of the Secondary Outcome Variables for Efficacy:

The secondary outcome variables for efficacy include: relaxation following maximum voluntary isometric contraction of the long finger flexors, repetitive stimulation relaxation time, rapid hand contraction and extension time, composite MVICT score derived by averaging the standardized (normalized) scores across the 10 individual muscles, grip strength derived by averaging the strength scores over the left and right hands, average MMT score derived by averaging the individual MMT scores across the 26 individual muscles, DEXA lean body mass, Modified Chronic Pain Scale scores, Brief Pain Inventory scores, holter monitor findings, IBS-IS scores, GSRS-IBS score, swallowing times, Purdue pegboard score, time to rise from a chair, time to walk 30 feet, Holter monitor data, SF-36 scores, and disease-specific health-related quality-of-life scores. These variables will be analyzed as described above for the primary outcome variable using repeated measures analysis of covariance, with the baseline value of the outcome variable used as a covariate. Again, depending on the nature of the outcome variable, data transformation or the use of nonparametric statistical methods may be required for analysis.

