#### Sample Size Considerations:

The primary outcome variable in this clinical trial will be the change from baseline to Month 6 in the mean distance walked during the six minute walk test. Using historical six minute walk test data in the DM1 population, we will have 80% power to detect a group mean change of 183 feet in distance walked over six minutes. This is based on a sample size of 18 per group (increased to 20 to account for the possibility of a 10% withdrawal rate), and a standard deviation of 190 feet. A two-sample T-Test Power Analysis is provided in Appendix A.

An important secondary outcome variable is the change from baseline to Month 6 in the time for relaxation of grip force following maximum voluntary isometric contraction of the long finger flexors.

This will be operationally defined as the time required to go from 90% of MVC to 5% of MVC averaged over three trials. In our randomized cross-over trials of mexiletine 150 mg three times daily and 200 mg three times daily, relaxation time from 90% to 5% of MVC was found to be the most sensitive measure of myotonia in terms of detecting a benefit of mexiletine. In the 18 subjects who completed the trial of 200 mg TID, the mean ( $\pm$  standard deviation) change (mexiletine – placebo) in this outcome was  $-1.34 \pm 1.42$  seconds. These data suggest that a sample size of 20 subjects per group will

provide 82% power to detect a group difference in mean response of -1.3 seconds in the proposed trial, using a t-test and a significance level of 5% (two-tailed).

Another important secondary outcome variable is the change from baseline to Month 6 in grip strength, averaged over the left and right hands. In our pilot randomized trial of troglitazone, grip strength data were available from 17 of the 20 randomized subjects at baseline and Month 8. The mean change averaged over both hands was -0.93 kg (reflecting mean changes of -1.32 kg in the left hand and -0.53 kg in the right hand) and the standard deviation of the changes was approximately 2.5 kg. Similar results were obtained at the Month 4 visit. These data suggest that a sample size of 20 subjects per group will provide 80% power to detect a group difference in mean response of 2.3 kg in the proposed trial, using a t-test and a significance level of 5% (two-tailed).

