The sample size will be increased as necessary to achieve a final group of 20 DM1 patients in both the mexiletine and placebo treatment groups. We anticipate that there may be a 10% rate of subject withdrawal based upon our recently completed FDA funded, 7 week, double-blind crossover trial of mexiletine in DM1 [Appendix A].

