#### 5. Interim Analyses for Safety and Efficacy

Interim analyses of safety data will be performed periodically throughout the project. While the safety of subjects will be the primary concern of the data safety monitoring board (DSMB), it is difficult to formulate precise stopping guidelines that would cover all of the possible situations that might arise. Adverse events, particularly serious adverse events such as deaths and hospitalizations, will need to be carefully considered by the DSMB in terms of treatment group imbalances. It is helpful to emphasize that our previous double-blind, randomized crossover trial of 20 DM1 patients treated with 150 mg three times daily of mexiletine for 7 weeks was completed without any significant adverse events; and, that a subsequent second double-blind, randomized crossover trial of 20 DM1 patients treated with 200 mg three times daily of mexiletine for 7 weeks was also completed without any significant adverse events. We do not anticipate encountering any expected side effect that based upon our advanced knowledge of mexiletine will constitute a reason to stop the study or specifically stop a given patient's participation. Severe confounding medical illness or severe trauma are reasons noted previously in this application for discontinuing patient participation. We perform serial laboratory studies throughout the course of the treatment trial. If the DSMB observes trends in all patients that suggest that a given value(s) is rising or falling 2-3 fold outside the normal range and is not known to occur in the usual clinical course of DM1, this finding will prompt a discussion of the need to stop the study. The same actions will occur if a serious medical illness develops in a significant portion of the DM1 patients receiving mexiletine which is not typically observed in the usual clinical course of a DM1 patient.

In addition, we will perform an interim analysis of the primary outcome variable after 50% of the trial participants (20 participants) have completed 6 months of follow-up. We will use an O'Brien-Fleming stopping boundary whereby the interim analysis will be performed using a significance level of 0.003 and the final analysis will be performed

using a significance level of 0.049 (two-tailed). This will ensure that the overall probability of a Type I error is controlled at 0.05.

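### The plan names only maximum likelihood for the primary model and gives no variance estimator, reference distribution or degrees of freedom, so the promised overall Type I error of 0.05 depends on unstated choices

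*Combined protocol and SAP*

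**What the plan says.** Under Statistical Analyses, the primary analysis consists of "fitting a repeated measures analysis of covariance model with treatment group as the factor of interest and the baseline value of the outcome variable" (the latter for adjustment), together with categorical month and treatment by month. It continues: "An unstructured covariance pattern will be used for model fitting. This model will be used to determine a 95% confidence interval". That interval is for the Month 6 treatment difference. The paragraph on missing data then says that the model "uses maximum likelihood to estimate the parameters of interest (treatment effects) using available data from all subjects", and goes on to the missing-at-random assumption.

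Under Interim Analyses for Safety and Efficacy, the plan has an "interim analysis of the primary outcome variable after 50% of the trial participants (20 participants) have completed 6 months of follow-up", tested at 0.003, and a final test at 0.049 (two-tailed). It adds: "This will ensure that the overall probability of a Type I error is controlled at 0.05".

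Under Sample Size Considerations, a t distribution appears, but only for power: "A two-sample T-Test Power Analysis is provided in Appendix A". The basis is 18 per group, raised to 20 for 10% withdrawal. The section later says: "The sample size will be increased as necessary to achieve a final group of 20 DM1 patients" in each arm.

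For secondary outcomes: "These variables will be analyzed as described above for the primary outcome variable using repeated measures analysis of covariance".

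The supplied text does not mention REML, Kenward-Roger, Satterthwaite or any other degrees-of-freedom rule.

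**The concern.** Maximum likelihood estimates the residual covariance without allowing for the fitted mean parameters, so its standard errors are slightly too small. In a large trial this is negligible. With 20 patients at the first look and 36 to 40 at the second it is not, particularly in the far tail where the 0.003 test operates. The reference distribution has a similar effect: a normal reference, or a t with too many degrees of freedom, gives p-values that are too small.

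The 0.003/0.049 pair keeps the overall error at 0.05 only if the p-values compared with it are accurate. At stake are the overall Type I error, the coverage of the Month 6 interval, and the protection that comes from fixing these choices before any data are seen, including at a look that can stop the trial. The secondary outcomes inherit the same gap, but no error rate is claimed for them, so no stated figure is breached there.

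**Working it through.** **1. Inputs.** From the documents: interim at 20 patients, levels 0.003 and 0.049 two-tailed, 18 per group (36) after withdrawal or 20 per group (40), 183 feet, SD 190 feet, two post-baseline visits, unstructured covariance. Assumed, because the documents do not give them: normal data and the Month 3 to Month 6 correlation.

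**2. The plan's own figure.** Critical values are z1 = 2.968 (0.003) and z2 = 1.969 (0.049). With correlation √0.5 between the looks, P(|Z1| > z1 or |Z2| > z2) = 0.04998; at an information fraction of 20/36 it is 0.0498. The boundary is correct when the variance is treated as known.

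**3. Closed-form check, one look at a time.** With complete data and a separate baseline slope per visit, the Month 6 contrast is an ordinary analysis of covariance with three mean parameters. The REML variance is RSS/(N-3) and the maximum likelihood variance is RSS/N, so the maximum likelihood standard error is √((N-3)/N) of the unbiased one. With c the t critical value on N-3 df, the true level of maximum likelihood with t is P(|t(N-3)| > c·√((N-3)/N)).

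| N | nominal | c | √((N-3)/N) | product | ML with t | REML, normal | ML, normal |
|---|---|---|---|---|---|---|---|
| 20 | 0.003 | 3.459 | 0.922 | 3.189 | 0.0054 | 0.0086 | 0.0141 |
| 36 | 0.049 | 2.044 | 0.957 | 1.957 | 0.0589 | 0.0574 | 0.0683 |
| 40 | 0.049 | 2.036 | 0.962 | 1.958 | 0.0578 | 0.0565 | 0.0662 |

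In this special case REML with t on N-3 df is exact.

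**4. REML with residual df.** Two visits and five mean parameters give 2N-5 df: 35 at N = 20 and 67 at N = 36. The critical values fall to 3.190 and 2.005. Referred to the correct t(N-3), the true levels are 0.0054 and 0.0532. REML alone therefore does not secure 0.05.

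**5. Both looks together.** The plan's model (one common baseline slope) was simulated under the null. Eight settings were used, 400,000 runs in all: 36 complete, 40 complete, or 40 with 4 missing Month 6 at the final look; in one setting, 10 further patients with Month 3 data only at the interim; correlation 0.5, with the two complete-data settings repeated at 0.3 and 0.8. The residual-df row comes from a second simulation (correlations 0.5, 0.7 and 0.85; 120,000 trials per scenario).

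| Variance and reference | Overall Type I error (range) |
|---|---|
| REML, t on N-3 df | 0.050 (0.048 to 0.052) |
| REML, Kenward-Roger | 0.050 (0.048 to 0.052) |
| REML, t on residual df | 0.055 to 0.057 |
| ML, t on N-3 df | 0.060 (0.057 to 0.061) |
| REML, normal | 0.061 (0.059 to 0.063) |
| ML, normal | 0.073 (0.070 to 0.075) |

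The Monte Carlo standard error is about 0.001 per setting, so most of the spread within a row is noise. With t on N-3, N-2 or N df, the second simulation gave 0.059 to 0.063 for ML and 0.050 to 0.052 for REML. ML with residual df gave 0.065 to 0.068.

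By look, ML with t on N-3 df gives 0.0049 to 0.0059 at the interim and 0.054 to 0.059 at the end. REML with the same t gives 0.0027 to 0.0036 and 0.047 to 0.051. Coverage of the nominal 95% interval is 94.0% to 94.5% against 94.8% to 95.2%.

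**6. Power.** With 18 per group the noncentrality is (183/190)·√(18/2) = 2.889 on 34 df. The critical value 2.032 (0.05) gives 80.2%, matching the stated 80%; 2.042 (0.049) gives 79.9%. With 20 per group at 0.049, power is 84.1%.

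**The case against.** The strongest reply is that the maximum likelihood sentence does not specify a test. It speaks of estimating treatment effects, sits between the handling of dropouts and the missing-at-random assumption, and explains why incomplete patients can be kept without imputation. It is silent on covariance estimation and standard errors. REML is a likelihood method and may have been what was meant, and the power calculation already uses a t. This stands. A reader might infer that the plan commits to a test with an error of 0.060, but the documents do not support that: the figure combines maximum likelihood variances with a t on N-3 df, a pairing the plan states no more than any other in the table.

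It is also fair that the effect is small, about one percentage point for maximum likelihood with t, and that the point estimate is essentially unaffected. The search covers only the supplied text. Appendix A is not in it, though its description as a power analysis makes it unlikely to settle the matter.

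What does not stand is that nothing needs saying. Maximum likelihood is the only estimator the plan names, and someone who programs it literally would exceed the stated rate. Nor is it enough to reply that REML with a t was intended, because the result still depends on the degrees of freedom.

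**Conclusion.** The concern holds as an incomplete specification with a small, conditional consequence. The supplied text does not settle how the primary p-value is computed, and the overall error can be anywhere from about 0.050 to about 0.073 depending on that choice. Only REML with a small-sample reference (Kenward-Roger, or a t on roughly N-3 to N df) delivers the 0.05 that the interim section says is ensured. If maximum likelihood variances are used with t on N-3 df, the excess is about one percentage point. The 0.073 for maximum likelihood with a normal reference is a worst case.

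A reader might also infer that the O'Brien-Fleming levels are wrong. They are not; they reproduce to 0.04998. These results assume normal data and correlations between 0.3 and 0.85, and they vary little across that range. Severity is low.

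**What to change.** In the missing-data paragraph of Statistical Analyses, replace the reference to maximum likelihood with restricted maximum likelihood and name a small-sample degrees-of-freedom method, to be used at both the interim and the final analysis. Kenward-Roger is suitable; a t on about N-3 df, with N the number of patients with Month 6 data, performs equally well here. Residual degrees of freedom and a normal reference should be ruled out. If this was already the intention, the sentence confirms it. The missing-at-random argument needs no change, since REML also uses all available data.

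The cost is one sentence and a standard software option. The final interval is about 4% wider than under maximum likelihood with t (√(36/33) = 1.044; √(40/37) = 1.040), and 7% to 8% wider than under maximum likelihood with a normal reference. Stated power is essentially unchanged because it already rests on a t-test.
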